their Skyn throughout the AA assessment period, but particularly during drinking episodes. A change in the revised application is that participants will not be able to see their current TAC at any time. However, for participants in the Full AA conditions, once the Skyn registers that they have reached .05 g/dl TAC, the app will prompt them to consider alternative transportation. Clickable links for local taxi/ride services will also be presented. Participants will be told that this prompt is based on their current TAC, and that it indicates it is not safe for them to drive, but will not be told the TAC trigger for this prompt. As noted, participants will wear the Skyn during their laboratory alcohol session. This will allow us to collect data on the accuracy of the Skyn's TAC estimates and, if necessary, develop individualized algorithms for estimating BrAC from TAC. Geospatial data. Throughout the AA assessment, participant location and movement data will be passively recorded on the study-provided smartphone. At the end of the AA period, this data will be combined with EMA data. When a participant reports drinking (or records a positive TAC), information about their drinking location, distance from home, travel using a motor vehicle, and what time they

returned home will be recorded. The most recent evidence for the accuracy of cellphone GPS systems indicate sufficient precision for our proposed use (Zandbergen & Barbeau, 2011). Using a much earlier generation of smartphones, they concluded that position estimation errors were uncommon, for example finding that horizontal location errors ranged from 5-21 meters in the least ideal conditions (static indoor testing). Data were more precise when moving outdoors, due to the clearer access to satellite data. Based on

this, we will use this geospatial information to provide a validity check on participant self-report. Discrepancies between participant selfreported location, use of motor vehicle, etc., will be probed during their next TLFB interview. As noted, [name] will provide the project with a database of GPS locations for all nearby licensed drinking establishments

Statistical Analyses and Power:

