Aim 1. Integrating laboratory and event-level predictors of AID. For Aim 1, we will employ a two-part (hurdle) model to test laboratory and AA predictors of AID. Part one of the model examines predictors of engagement in AID (or driving after any drinking). For this part of the model, we will employ a mixed logistic model examining factors that are predictive of a dichotomous variable indicative of whether, for a given drinking event, a participant drives after drinking alcohol. The second part of the model will employ a Gaussian linear mixed model, and examines predictors of a participant's TAC/BrAC level at the time of driving for drinking events where driving is reported. This analytic approach provides us with both increased flexibility and precision in our analyses. For example, we will be able to identify predictors of driving after any drinking as well as predictors that may be specific to driving at higher TAC. We believe that this flexibility is an important improvement to our approach in the revised application. For example, Hypothesis 1.3 will examine whether contextual factors increase the influence of AID risk factors on the likelihood of AID. Hypothesized contextual factors are based on studies demonstrating that drinking location (fewer miles to home; Kelley-Baker et al., 2013) and venue (drinking in restaurants; Gruenwald et al., 2002) are associated with increased AID risk. Our two-part model will allow us to test whether, for example, drinking venue increases the effect of AID risk factors for driving after any drinking, while drinking location increases the effect of AID risk factors when predicting driving at higher TAC/BrAC. In addition to examining TAC/BrAC at time of drinking as a continuous attribute, our approach will allow us to examine rational cutpoints for TAC – specifically, we will test models for cutpoints of TAC/BrAC of the current U.S. legal limit (.08) and NHTSA's proposed limit (.05). Research Strategy Page 68 Contact PD/PI: [name] Both models will have two levels, comprised of drinking events within participants. We will estimate models via both Maximum Likelihood methods and Generalized Estimating Equations; the former method can result in more accurate parameter estimates in certain situations (Stroup, 2013), whereas the latter method can be more flexibly extended to assumption violations (e.g., variance heterogeneity). Modeling will proceed by first fitting baseline GLMMs that establish associations between lower-level measures and the DV. The lower-level measures will be at the event level (including such variables as drinking venue), so they will directly address Hypothesis 1.2. Once these lower-level associations are established, we will then incorporate laboratory measures to address Hypothesis 1.1, followed by interactions to address Hypothesis 1.3. For example, consider studying the relationship between event-level impulsivity and AID. We will first person-center the impulsivity variable, so that the associated regression weight provides information about the effect of impulsivity as a participant departs from his/her mean level of impulsivity. We will then establish an association between impulsivity and AID using a two-level logistic model, where multiple eventlevel variables are included as IVs. The models will account for individual differences in associations between the event-level variables and AID, and they will be further extended (using level-2 IVs and cross-level interactions) to study the laboratory-based effects and moderation effects from Hypotheses 1.1 and 1.3. We will fit multiple versions of the models using different subsets of IVs, in order to establish that effects are robust to choice of predictors. This is important because unmodeled heterogeneity (resulting from omitted predictor variables) can adversely impact model estimates (Mood, 2009). To estimate power associated with these models, we adopted a simulation-based approach (Gelman & Hill, 2007). This involved generating artificial data from an assumed true model, fitting the proposed GLMM to each artificial dataset, and computing power based on the results. To estimate our power to detect an association between event-level impulsivity and AID, we specified parameter values for the true model based on previous studies. First, based on pilot data, we assumed that participants report driving following 15% of drinking events. We also assumed that each 5- point increase in impulsivity (as measured by delay discounting) was associated with (i) a 10% increase in the odds of driving after drinking (the low end of observed effect sizes for core study constructs) and (ii) a BrAC increase of .01, with random participant effects included in “maximal” models (Barr et al., 2013). In using these parameter values along with the anticipated sample sizes, our estimated power to detect these

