
associations is .91 in the logistic model and .99 in the linear mixed model. If Aim 2 is realized, then we can only use half of the Full AA group (the half that does not receive AA for the first six weeks), along with the

MA control group, to assess raw associations between lower-level variables and AID. In this case, we estimate power of .85 and of .99 to detect the associations (using the same values as above with a reduced sample size). We computed additional power estimates for moderation Hypotheses 1.3, using both the logistic model (where AID is a binary DV) and the Gaussian model (where TAC/BrAC is the DV). We assumed that Aim 2 was not realized, reducing the overall number of participants that we could enter into the analysis. For the logistic model, we assumed (as above, based on pilot data) that each 5-point increase in impulsivity was associated with a 10% increase in the odds of driving after drinking. We further assumed that this relationship was moderated by drinking venue, such that the relationship was diminished when participants were drinking at a restaurant. Under this scenario, power was .77 for the moderation

effect. For the Gaussian model, we assumed (as we did above) that each 5-point increase in impulsivity was associated with a mean BrAC increase of .01. We further assumed that this relationship was moderated by drinking location, such that the relationship was absent if a person was drinking 10 or more miles from home. Under this scenario, power was .96 for the moderation effect. Aim 2. Test potential effects of AA on AID behavior and intentions. For Aim 2, the study design affords us multiple manners in which we can examine the potential of mobile technology as an intervention for AID. We can estimate the effect of AA prospectively, examining whether or not AID changes from before a participant receives AA to after. We can also estimate the effect across experimental groups, examining whether or not AID differs between the groups with Full AA and the MA control group. To address this question, we will again employ the two DVs of driving after drinking and TAC in separate GLMMs (where drinking events are nested within participants). The IVs in each model will be dummy variables that are related to each participant's condition and to the time within the study. Specifically, the dummy variables will reflect whether or not the

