individual is currently receiving AA, as well as whether or not the individual ever previously received AA. This will allow us to disentangle the effect of currently receiving AA from effects that may last after the individual has received AA. In computing power, we assumed 100 participants receiving AA at differing times (as described in Overview of Proposed Work) coupled with 100 participants in the control group. We further assumed that (i) active reception of AA reduces driving after Research Strategy Page 69 Contact PD/PI: [name] drinking from an average of twice per month to an average of 1.5 times per month (with individual differences in this effect), and (ii) active reception of AA reduces TAC of driving events by an average of .01. In employing assumption (i) in a logistic mixed model, we obtained a simulation-based power estimate of .79 to detect an intervention effect of active AA. In employing assumption (ii) in a Gaussian linear mixed model, we obtained a simulation-based power estimate of .97 to detect the intervention effect.

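### Aim 2 compares TAC only among drives that AA is expected to thin out, so that coefficient is not a separate randomised effect; counting drives at TAC .05 and .08 per observed day is a cheap improvement

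*Combined protocol and SAP*

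**What the plan says.** Under Statistical Analyses and Power, Aim 1 sets out a two-part model. Part one is a logistic mixed model for whether a drinking event is followed by driving. Part two is a Gaussian mixed model for the participant's TAC/BrAC "level at the time of driving for drinking events where driving is reported".

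Aim 2 carries these outcomes over: "we will again employ the two DVs of driving after drinking and TAC in separate GLMMs". The predictors are indicators for receiving AA now and for having received it before.

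The Aim 2 power paragraph makes two assumptions about active AA. Driving after drinking falls: "drinking from an average of twice per month to an average of 1.5 times per month". And "active reception of AA reduces TAC of driving events by an average of .01". For the first: "In employing assumption (i) in a logistic mixed model, we obtained a simulation-based power estimate of .79". For the second: "in a Gaussian linear mixed model, we obtained a simulation-based power estimate of .97 to detect the intervention effect".

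The section on Transdermal Alcohol Concentration describes the prompt given in the Full AA conditions: "once the Skyn registers that they have reached .05 g/dl TAC, the app will prompt them to consider alternative transportation". Participants are told that the prompt reflects their current TAC and that "it indicates it is not safe for them to drive".

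The text available describes no Aim 2 outcome per unit of time, and no allowance for AA changing which drives enter the TAC model. Cutpoints of .05 and .08 appear under Aim 1 only.

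**The concern.** Randomisation balances people, not drives. Whether a drive happens is decided after randomisation, and AA is meant to influence it. The TAC model therefore compares the drives that remain under AA with drives made without AA. Because the prompt is tied to TAC, the averted drives may have had higher TAC than the rest. Mean TAC among the remaining drives would then fall with no individual drive changed.

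A lower mean could be reported as people driving at lower TAC, when it reflects the same averted drives already counted in the logistic model. If the averted drives were instead the lower-TAC ones, a real fall would be partly hidden. In a model meant to predict driving (Aim 1) the conditioning is reasonable; for an intervention question (Aim 2) it needs a caveat and a companion analysis.

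**Working it through.** **The plan's own figures.** Neither power can be reproduced exactly, because TAC variance, random-effect variances, alpha and the full layout are not in the text.
- For .79: a simulated logistic mixed model (15% of drinking events followed by driving, as in Aim 1, against 11.25%) gave .83 to .90 with an assumed 12-week layout (50 early AA, 50 delayed AA, 100 control) and .42 to .73 with six weeks only. So .79 is attainable.
- For .97: with independent drives it implies a TAC SD of about .024 to .034.

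**The selection identity.** Inputs from the Aim 2 power paragraph: 2 to 1.5 drives per month, so 1 - 1.5/2 = 25% averted. Let m be the mean TAC of all drives and a the mean TAC of averted drives.
- Mean of remaining drives = (m - .25a)/.75.
- Shift = (m - .25a)/.75 - m = -(a - m)/3.

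**Crude size under assumed TAC.** Assume normal TAC with mean m and SD s, and let a share w of averted drives lie above .05. With k = (.05 - m)/s:
- mean above .05 = m + s·φ(k)/P(above)
- mean below .05 = m - s·φ(k)/P(below)
- a = w·(mean above) + (1 - w)·(mean below)

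| m, s | share of drives above .05 | w = 1 | w = .9 | w = .75 |
|---|---|---|---|---|
| .05, .02 | .50 | -.0053 | -.0043 | -.0027 |
| .05, .03 | .50 | -.0080 | -.0064 | -.0040 |
| .06, .02 | .69 | -.0034 | -.0023 | -.0006 |
| .06, .03 | .63 | -.0060 | -.0044 | -.0019 |
| .07, .02 | .84 | -.0019 | -.0007 | +.0011 |
| .07, .03 | .75 | -.0043 | -.0026 | .0000 |

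The planned effect is -.01. The largest gap a - m in the table is .024 (3 × .0080).

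**Size in a mixed model.** The plan fits participant effects, which absorb part of the crude shift. A random-intercept model was simulated with the 12-week layout, mean TAC .05, ICC .3 (assumed), a 25% cut in drives and no change in any drive's TAC (80 to 100 runs per setting).
- Only drives at or above .05 averted: -.004, -.006 and -.008 at SD .02, .03 and .04; a significant fall in about 60% of runs.
- Averting twice as likely at or above .05: -.0015 and -.002 at SD .02 and .03; significant in about 10%.
- Random averting (SD .02): no fall; significant in 2.5%, as expected by chance.

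**Power of the added outcomes.** This assumes that Aim 1's 15% carries over and scales from the plan's .79.
- Odds ratio = (.1125/.8875)/(.15/.85) = .718. Noncentrality for .79 = .806 + 1.96 = 2.766.
- Any drive per day: ratio to the logistic test = [ln .75/√(1/.15 + 1/.1125)]/[ln .718/√(1/.1275 + 1/.0998)] = .93. Then 2.766 × .93 = 2.57, and power = Φ(2.57 - 1.96) = .73.
- Simulated Poisson mixed model, 12-week layout: .72 to .88 as the between-person SD of the log rate goes from 1.0 to 0.5.
- Drives at or above .05: replace .15 and .1125 by p0 = .15 × share above .05 and p1 = p0 - .0375w. Best case (share .50, w = 1): .075 to .0375, power .97. Worst case (share .84, w = .75): .126 to .098, power .55.

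**The case against.** The plan declares its two-part form openly and words the assumption as TAC of driving events. Nothing in it claims that individuals will drive at lower TAC. That stands: the plan conceals nothing. But declaring the conditioning does not turn the second part into a randomised comparison, and the power paragraph still calls its coefficient the intervention effect.

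The size is assumed, and mild or random selection gives little or nothing. That also stands. A reader might infer that selection alone could produce the whole planned fall of .01. This needs averted drives .03 above the overall mean, which no cell of the assumed range reaches. Averting exactly the top quarter of drives would do it (a shift of 0.42 SD, so .01 at SD .0236), but nothing in the documents suggests selection that sharp.

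A rate of drives at any TAC does not repair the TAC contrast. Correct; it is the counts at the cutpoints that carry TAC level without conditioning on driving. Nor is the rate free of post-randomisation influence: observed days depend on compliance, counts at a cutpoint depend on wearing the Skyn, and MA control completes shorter reports with no AID-specific questions. These limits remain and shape the fix.

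**Conclusion.** The point holds as a cheap improvement. The AA coefficient for TAC among drives mixes any real change with a change in which drives occur, so it should not be read as a separate randomised effect. Neither direction nor size can be settled from the documents. Under the assumed distributions the crude shift runs from +.0011 to -.0080. In the simulated mixed model it was -.004 to -.008 if only drives at or above .05 are averted, about -.002 if averting is twice as likely there, and none if averting is random.

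Two stronger inferences are not supported. First, the stated .79 and .97 are not shown to be wrong; they depend on variances and a layout that are not in the text. Second, it cannot be said that the study has no outcome per unit of time anywhere, because the Overview of Proposed Work, to which Aim 2 refers, was not available to check.

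**What to change.** Keep both planned models. Report the TAC model as descriptive and conditional on driving.

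Add a supporting Aim 2 analysis in all randomised participants, including those with no drives:
- drives at TAC .05 or above and at .08 or above (the Aim 1 cutpoints) per observed day, for example a count mixed model with log observed days as offset;
- drives at any TAC per observed day alongside.

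Use one driving definition in all groups, built from items that every arm supplies: the morning transportation report and location data. Report observed days, drinking events and drives without a TAC reading by condition. Show the cutpoint results with those drives counted as above, and again as below, the cutpoint.

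The cost is analysis wording; no new data are needed. The downside is extra supporting outcomes and power of about .73 by formula for the any-drive rate (.72 to .88 in simulation) and about .55 to .97 for drives at or above .05, depending on how many averted drives exceed .05. Unequal compliance between groups remains a limit, because observed days arise after randomisation.
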